1.0 BACKGROUND AND RATIONALE

Advances in 3D breast imaging. Three-dimensional imaging, extensively utilized to provide objective outcome measures in craniofacial surgery, has been adapted for evaluation of the breast. Three-dimensional images of the breast can be used to facilitate patient education, surgical planning, as well as both a research and marketing tool by plastic surgeons. Over the past few years, investigators have identified breast measurements calculated from computerized renderings of three-dimensional photographs and documented changes in these measurements following surgical procedures such as breast reduction, breast reconstruction with implants, and breast augmentation. Changes in these parameters after operative intervention have enabled surgeon scientists to compile objective quantitative breast data, or "mammometrics" (1). Mammometric data can be statistically analyzed, longitudinally evaluated in the same patient over time, and correlated with other quantitative data including patient reported outcomes. Some of the useful mammometric measurements that can be used to quantify and compare pre- with postoperative breast surgery include total and split breast volumes, distances from the low breast crease to the nipple, and projection of the breast and nipple from the chest wall among others.

Outcomes research in plastic and reconstructive surgery is more likely to focus on patient reported outcomes than survival. While the plastic surgery literature is replete with surveys focused on judging patient satisfaction, they are infrequently validated or comprehensive. The Breast Q has been established as a validated instrument to provide a quantitative measure of the unique features of patient reported outcomes following breast surgery. This instrument represents the most comprehensive and specific quantitative method for patient self-assessment following breast surgery. Recently, McCarthy and colleagues published, for the first time, patient satisfaction in 41 patients who underwent breast augmentation and were evaluated with the Breast Q. This study found statistically significant improvements following breast augmentation in the "satisfaction with breasts" – 14 item scale, "psychological well-being" – 9 item scale, and "sexual well-being" – 5 item scale. This study does not, however, include information on either the benefits of 3D imaging or the mammometric parameters most closely associated with improved satisfaction. Interestingly, the core scale "satisfaction with care" was not evaluated in this study. While this particular core scale may not have been relevant to a study looking at the overall benefits of breast augmentation, we suspect that it may be highly relevant to the aesthetic surgery patient where the consultation experience is more likely to impact overall patient satisfaction.

This study will evaluate the impact of incorporating 3D imaging during preoperative consultation on patient reported outcomes in primary breast augmentation surgery. 3D imaging can be used to facilitate patient education and surgical planning in the context of breast augmentation. The purpose of this study is to utilize the most objective assessment available for assessing patient satisfaction with breast augmentation - the Breast Q - in a prospective randomized trial. We will evaluate whether 3D imaging used in consultation 1) can improve patient reported outcomes, and 2) whether there are measurable mammometric parameters that are associated with improved patient satisfaction and 3) if utilizing 3D imaging in the pre-operative consultation significantly influences final mammometric parameters compared to patients receiving a traditional consultation that does not involve 3D breast surgical simulation.

It is hoped that patients of surgeons that utilize this technology in the preoperative consultation will have significantly higher Breast Q breast augmentation module scores 6 months after surgery. "Satisfaction with care" - one of six core scales within the Breast Q - will be particularly impacted by using 3D image simulation in the consultation experience. Additionally, it is thought that superomedial pole fullness and central nipple position as quantified with mammometrics that

the 3D imaging can provide will be associated with higher Breast Q scores, especially the “satisfaction with breasts” items.

This study will represent one of the first randomized control trials performed to address patient satisfaction with breast augmentation.

2.0 OBJECTIVES

2.1 Primary Objective

To establish whether 3D imaging used in breast augmentation consultation can improve patient reported outcomes.

2.2 Secondary Objective

To determine if measureable mammometric parameters are associated with improved patient satisfaction.

3.0 PATIENT SELECTION

3.1 Inclusion Criteria

- 18 years of age or older
- Scheduled for elective breast augmentation cosmetic procedure

3.2 Exclusion Criteria

- Cognitively unable to provide informed consent
- Breast reconstruction for malignancy

3.3 Inclusion of Women and Minorities

Due to the nature of the surgical procedure, men are excluded from participation in this study. Members of all races and ethnic groups are eligible for this trial.

3.4 Inclusion of Non-Randomized Cohort

Patients who refuse the option of randomization but otherwise meet the inclusion and exclusion criteria will be offered participation in this study as part of a non-randomized cohort. All aspects of the study as described in the protocol will be followed with exception of the randomization will be followed.

4.0 TREATMENT PLAN

4.1 Preoperative Evaluation

Standard preoperative evaluation will be conducted on all patients. It is routine practice in cosmetic surgery to take baseline pictures and measurements. Both 2D and 3D photography will be performed on all patients.

4.2 Randomization

100 patients will be recruited in the randomized cohort. Randomization will be performed by a Research Patient Coordinator and the patient assigned to the control group or the intervention group. Randomization will only occur after the patient has signed the informed consent and will be documented in the case report file as well as communicated to the treating surgeon.

Intervention group

In the intervention group, in addition to standard preoperative evaluation, 3D image simulation will be performed.

Control group

In the conventional group, only the standard preoperative evaluation will be performed.

Non-Randomized cohort

In the non-randomized cohort, the patient can choose to have the standard evaluation with the addition of the 3D image simulation or not based on discussion with their surgeon.

Minimizing measurement bias

Blinding of the patient or surgeon will not be possible due to the need for the 3D imaging simulation to be openly discussed and viewed prior to the operation for patients randomized to 3D intervention and for the nonrandomized cohort.

All subjects will be administered the Breast Q questionnaire prior to surgery regardless of assigned group. The questionnaire will take approximately 5-10 minutes of time to complete.

4.3 Operative Procedure

The elective surgical procedure will be conducted as planned.

4.4 Postoperative Care

The postoperative management is standard of care for all patients who undergo breast augmentation procedure and will not be altered by their participation in this study.

4.5 Duration of Follow-Up

Patients will be followed for 6 months following their surgical procedure. Postoperative complications and adverse events will be closely monitored. Patients will be followed until resolution or stabilization of the adverse event.

At the 6 month follow-up appointment, routine postoperative 2D and 3D images will be taken for comparison to baseline. As part of this research study, the Breast Q questionnaire will be re-administered to the subject.

4.6 Criteria for Removal from Study

If at any time the constraints of this protocol are considered to be detrimental to the patient's health and/or the patient no longer wishes to proceed with the protocol intervention, the patient should be removed from the study and the reason(s) for discontinuation documented in the case report forms.

Otherwise, the patient will receive the intervention and be followed as described.

5.0 ADVERSE EVENT REPORTING

5.1 Adverse Events

Definition: any unfavorable medical occurrence in a human subject including any abnormal sign, symptom, or disease.

Attribution (relatedness), Expectedness, and Seriousness: the definitions for the terms listed that should be used are those provided by the Department of Health and Human Services' Office for Human Research Protections (OHRP). A copy of this guidance can be found on OHRP's website: <http://www.hhs.gov/ohrp/policy/addevntguid.html>

5.2 Reporting to the Human Research Protection Office (HRPO) at Washington University:

All HRPO guidelines for reporting unanticipated problems will be followed.

6.0 DATA AND SAFETY MONITORING

The study principal investigator and Research Patient Coordinator will closely monitor for adverse events on an ongoing basis. Once the principal investigator or Research Patient Coordinator becomes aware of a research related adverse event, the AE will be reported to the HRPO according to institutional guidelines.

6.1 Potential risks

A possible breach of confidentiality of study data is an unlikely risk.

6.2 Minimization of risks

PHI will be collected and include the patient's name, date of birth, date of surgery and date of follow-up. The patient's name and other identifiers will be kept in a password-protected database in which access will be granted to only the research team.

Participants will be assigned a study number and after the data is collected, all identifiers with the exception of date of birth will be removed.

All study papers with and without identifiable study information will be kept in a locked file cabinet in a locked room in a locked office for the duration of the study data collection period. All information will be entered into a database. The database is secure, saved on a firewall protected network, and password protected. All hard copies of identifiable information will be disposed of by shredding after the information is reviewed and locked into the database, the analysis has been made, and the report has been written, and one year has passed from the date of publication.

6.3 Potential benefits

Direct benefit to the patient is unknown. The patients randomized to receive the 3D simulation of what their implants are anticipated to look like may feel greater satisfaction with the aesthetic results after their surgery.

7.0 STATISTICAL CONSIDERATIONS

7.1 Study Endpoints

Primary endpoint

BREAST Q Augmentation Module. This includes 6 core items, each with several sub-items. Of the 6 core items, 3 are recently shown to statistically significantly improve in patients undergoing breast augmentation: 1) satisfaction with breasts 2) psychological well-being 3) sexual well being. A fourth, 4) satisfaction with care, however, may be particularly relevant to the discerning aesthetic surgery patient using 3D imaging in consultation. The other core items in this instrument are 5) physical well-being and 6) satisfaction with overall outcome which will also be recorded.

Secondary endpoints

All patients will undergo standard 2D as well as 3D imaging before and after surgery. During consultation, and in the postoperative period, reviewing 3D imaging and morphing software will be unique to the experimental group. 3D imaging from all patients will be used to obtain mammometric data. Pre- , and post- op mammometric data (volumes, vectors, surface distances, anatomic landmarks), as well as the measurable change in these parameters before and after surgery will be correlated with changes in Breast Q patient reported outcomes scores. This will enable us to identify particular mammometric parameters that are a) associated with improved patient reported outcomes and b) determine whether certain mammometric parameters are significantly different in patients who had 3D image simulation as part of their preoperative consultation relative to those that did not.

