7.3 Sample Size

Appropriate sample size is calculated based on assumption of difference of 20 percent in patient satisfaction as compared with the control group. This difference is considered clinically relevant based on previous similar studies. A sample size of 100 patients (50 in each group) is considered sufficient to prove this difference, if present (alpha error set at 0.05, power>99 percent).

Approximately 75 patients per year undergo a breast augmentation procedure at Washington University Medical Center. The estimated time frame to randomize 100 patients is approximately 24 months.

Non-randomized cohort

Up to 50 patients will be included in the non-randomized cohort.

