7.4 Data Analysis

Data analysis for this study will be descriptive in nature. Demographic and clinical characteristics of the sample, as well as post-surgery complications will be summarized using descriptive statistics and the confidence intervals will also be provided.

[figure not shown]
Patients assigned to the intervention group (3D simulation) will be compared with those who had conventional techniques using χ^2 tests for categorical variables and Student's t-tests for continuous variables. For the t-tests equal variances were not be assumed, unless significant by Levene's test. Mann-Whitney U tests will be utilized for non-normally distributed variables. Two-tailed P values 0.05 will be considered statistically significant.

Multivariate analyses for Breast Q scores, mammometric parameters, and patient satisfaction will be performed using binary logistic regression and linear regression models to examine the relationship between intervention groups and examined outcomes and to identify potential confounders. The results of multivariate analyses will be expressed as odds ratios with corresponding 95% confidence intervals. All analyses will be performed using SPSS 20.0 statistical software (SPSS Inc. Chicago, IL).

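### The primary endpoint is a six-scale questionnaire with no primary scale, success rule or multiplicity control, so the stated alpha and power belong to no defined test

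*Protocol*

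**What the plan says.** Protocol 7.1 defines the primary endpoint as "BREAST Q Augmentation Module. This includes 6 core items, each with several sub-items". Under that heading it singles out four scales: satisfaction with breasts, psychological well-being, sexual well-being and satisfaction with care. It then adds physical well-being and "satisfaction with overall outcome which will also be recorded". No scale is called primary.

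Protocol 7.3 bases the sample size on an "assumption of difference of 20 percent in patient satisfaction as compared with the control group" and calls 50 patients per arm "sufficient to prove this difference, if present (alpha error set at 0.05, power>99 percent").

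Protocol 7.4 opens with "Data analysis for this study will be descriptive in nature". It then sets χ², t and Mann-Whitney comparisons between arms, states "Two-tailed P values 0.05 will be considered statistically significant", and adds "Multivariate analyses for Breast Q scores, mammometric parameters, and patient satisfaction will be performed" by logistic and linear regression.

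Protocol 1.0 hopes that patients given 3D imaging "will have significantly higher Breast Q breast augmentation module scores 6 months after surgery" and expects satisfaction with care to be affected in particular. The primary objective in 2.1 speaks only of patient reported outcomes in general.

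The SAP mentions the Breast Q only as a Q-Score, in its sentence on correlations. Its patient-level comparisons by t-test or Wilcoxon test name no outcome.

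**The concern.** A trial that sets out to establish a benefit needs one identifiable test, or a stated family of tests with a rule, to carry its alpha. Here six scales share the primary heading and each may be tested at 0.05. The rule for success could be one scale, all scales or a total score, and nothing prevents that choice being made after the results are seen. Apart from the recorded expectation about satisfaction with care, a reader of the final report could not tell a planned primary result from the best of four or six. Pre-specification matters more than usual here because protocol 4.2 says neither patient nor surgeon can be blinded and the outcome is self-reported.

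**Working it through.** **1. The plan's own figure.** Inputs are 50 per arm and power above 99% (7.3), two-tailed 0.05 (7.4) and a 20 percent difference (7.3). No SD, control rate, scoring range or scale is given, so the figure can be neither confirmed nor refuted.

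- If 20 percent means 20 points on a 0–100 scale (assumption), 99% power needs SD ≤ 20 / [(1.960 + 2.326) × √(2/50)] = 20 / 0.857 = 23.3.
- If it means 20 percentage points between proportions, power is about 52–93% across control rates.

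The power claim therefore cannot be used to work back to a scale.

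**2. Looking for a defined primary test.**

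- 7.3, patient satisfaction: three of the six scales carry satisfaction in their name (breasts, care, overall outcome).
- 7.4 lists Breast Q scores and patient satisfaction as separate outcomes, so the two terms are not plainly the same thing.
- 1.0, module scores, and SAP, Q-Score: neither is defined as a summary score.
- 1.0, satisfaction with care: an expectation that no section turns into the primary test. The next sentences link the mammometric hypothesis to satisfaction with breasts instead.
- Outcome form: the questionnaire is given before surgery and at 6 months (4.2, 4.5), and the plan does not say whether the arms are compared on the 6-month score or on change.
- Test: t-test, rank test and regression are all listed.

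**3. Error under each possible rule.** Each test is two-sided 0.05, so 2.5% falls in the direction favouring 3D. The correlations ρ, taken as equal between all scales, are assumed. With k scales and no true effect:

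- any one scale: 1 − ∫ φ(x) Φ[(1.96 − √ρ·x)/√(1−ρ)]^k dx. At ρ = 0 this is 1 − 0.975^4 = 0.0963 and 1 − 0.975^6 = 0.1409.
- all scales: ∫ φ(x) {1 − Φ[(1.96 − √ρ·x)/√(1−ρ)]}^k dx.

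| Rule (false result favouring 3D) | Four scales | Six scales |
|---|---|---|
| One pre-named scale or single score | 2.5% | 2.5% |
| All must differ, ρ = 0.8 | about 0.5% | about 0.3% |
| Any one, ρ = 0 | 9.6% | 14.1% |
| Any one, ρ = 0.5 | 7.8% | 10.4% |
| Any one, ρ = 0.7 | 6.5% | 8.2% |
| Any one, ρ = 0.8 | 5.7% | 6.9% |

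Simulated t-tests with 50 per arm agree for the any-one rule: 9.6% and 5.6% (four scales), 13.9% and 7.0% (six), at ρ = 0 and 0.8. Counting both directions, the any-one figures are 11.4–18.5% (four) and 13.9–26.5% (six), against 5%.

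**4. What control would cost.** The first Holm step tests at 0.05/k. Under no effect it rejects at most 4.9% of the time, two-sided, for four or six scales. Power for one given scale comes from the noncentral t distribution with 98 df and noncentrality (20/SD) × √(50/2), again taking 20 percent as 20 points:

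| Assumed SD | Unadjusted | Four scales | Six scales |
|---|---|---|---|
| 20 | 99.9% | 99.2% | 98.9% |
| 25 | 97.7% | 92.5% | 90.2% |
| 30 | 91.0% | 78.3% | 73.8% |

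If several scales respond, the fair comparator is the any-one unadjusted rule that Holm would replace. By simulation at SD 30, for correlations 0.7 to 0.5, the chance of at least one rejection favouring 3D is:

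| Scales, number responding | Any one, unadjusted | Holm | Loss |
|---|---|---|---|
| Six, two | 96.0–97.3% | 84.3–87.4% | about 10–12 points |
| Six, four | 98.2–99.3% | 91.0–94.7% | about 5–7 points |
| Four, two | 96.0–97.2% | 87.8–90.4% | about 7–8 points |
| Four, four | 98.3–99.3% | 93.3–96.3% | about 3–5 points |

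**The case against.** Four replies deserve weight.

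- The plan calls its analysis descriptive. That shows the plan is inconsistent with itself, but it does not remove the gap: a significance threshold follows in the same section, and 7.3 speaks of proving a difference.
- Satisfaction with care could be read as the implied primary scale. The expectation in 1.0 is genuine and would help an honest reader, but 7.1 lists that scale fourth and says only that it may be particularly relevant.
- Module scores and Q-Score could hint at one total score, which would keep the error at 2.5%. Neither document defines such a score, so the reading is open but not established.
- The any-one-scale rule is nowhere in the documents. This stands. A reader might infer from the table that the trial runs a 6.9–14.1% false-positive risk. The documents do not support that, because a stricter or single-score rule is equally compatible with the text and gives 2.5% or less.

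**Conclusion.** The concern holds as a missing definition. The stated alpha of 0.05 and power above 99% are attached to no identifiable primary test, so success or failure on the primary objective cannot be determined from the plan. That conclusion needs no assumption. The size of any inflation does: depending on the unstated rule, the chance of a false result favouring 3D runs from well below 2.5% to 14.1%, the upper end requiring six uncorrelated scales and an any-one rule. It would be wrong to call the inflation known. It would also be wrong to infer that multiplicity control is free when several scales respond. Holm power then looks close to that of one unadjusted scale, but against the any-one rule the loss at SD 30 is about 3 to 12 points. The matter should be settled before any between-arm Breast Q result is analysed.

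**What to change.** Amend 7.1, 7.3, 7.4 and the SAP before any between-arm Breast Q analysis, in one of two ways.

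1. **Preferred.** Name one scale as primary; the choice is the sponsor's. State whether the outcome is the 6-month score or the change from baseline, name the one primary test, and test it at two-sided 0.05. Say in 7.3 that this scale is what patient satisfaction means. Make the other scales secondary under Holm, and state that they do not decide the primary objective.
2. **Alternative.** State which four or six scales are primary and apply Holm at a familywise two-sided 0.05. Count the objective as met if at least one scale is rejected in favour of 3D, and limit the conclusion to the scales rejected. The outcome form and test still need to be fixed for each.

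In either case, reconcile the descriptive label in 7.4 with the significance tests there and with the language of proof in 7.3.

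The cost is text only, with no new patients or data. Option 1 loses no power relative to a single-scale test at 0.05, but gives up the chance of success on another scale. Under option 2, if only one scale responds, power for it falls by about 1 / 5 / 13 points (four scales) or 1 / 8 / 17 points (six) at assumed SD 20 / 25 / 30. If several respond, the losses are those in the last table of the working.

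### Section 7.1 reserves a postoperative 3D review for the experimental arm, and nothing visible requires the 6-month Breast Q to come before it

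*Protocol*

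**What the plan says.** In the secondary-endpoints text of Protocol 7.1: "During consultation, and in the postoperative period, reviewing 3D imaging and morphing software will be unique to the experimental group". This gives the experimental arm two exposures, one at consultation and one after surgery.

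The rest of the protocol describes one:

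- Study question (1.0): "This study will evaluate the impact of incorporating 3D imaging during preoperative consultation on patient reported outcomes in primary breast augmentation surgery".
- Hypothesis (1.0): patients of those surgeons who "utilize this technology in the preoperative consultation will have significantly higher Breast Q breast augmentation module scores 6 months after surgery".
- Primary objective (2.1): "To establish whether 3D imaging used in breast augmentation consultation can improve patient reported outcomes".
- Arm definition (4.2): "In the intervention group, in addition to standard preoperative evaluation, 3D image simulation will be performed".
- Blinding (4.2): "Blinding of the patient or surgeon will not be possible", the reason given being "the need for the 3D imaging simulation to be openly discussed and viewed prior to the operation".
- Postoperative care (4.4): management after surgery "will not be altered by their participation in this study".

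Section 4.5 schedules both the postoperative 2D and 3D images and the repeat Breast Q for the 6-month appointment. The SAP does not mention postoperative review.

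**The concern.** The primary endpoint is the Breast Q Augmentation Module, completed by patients who know their arm. Its scales include satisfaction with breasts, with care and with the overall outcome. Being shown one's own 3D images or morphing software after surgery could plausibly affect such ratings, and under 7.1 only one arm would have that experience.

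If it happened before the questionnaire, the trial would be testing preoperative plus postoperative 3D review. The stated question is narrower: whether 3D imaging in the consultation improves patient-reported outcomes. A positive result could then be reported as a benefit of the consultation when part or all of it came from the later review.

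**Working it through.** The plan gives no figure on this point, so the check is a comparison of texts followed by a short identification argument.

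**Step 1. Where each section places the 3D exposure.**

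| Place in the protocol | Exposure described | Postoperative review? |
|---|---|---|
| 1.0, study question and hypothesis | Preoperative consultation | No |
| 2.1 | Consultation | No |
| 4.2, arm definition | Added to the preoperative evaluation | No |
| 4.2, blinding | Viewed before the operation | No |
| 7.1, sentence quoted above | Consultation and postoperative period | Yes |
| 7.1, closing line, part (b) | Groups defined by simulation in the preoperative consultation | No |
| Appendix B, 3D Simulation row | Marked under Intervention only; blank at Screening and at 6 months | No |

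One sentence stands against all the others, including the end of its own paragraph.

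**Step 2. Who reviews, and when.** The sentence does not say. Patient review is the natural reading, because the same sentence covers the consultation, but that is an inference. No visible text dates the review. Appendix A, the study timeline, appears only as a heading, so it cannot be checked.

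**Step 3. Which review could precede the 6-month Breast Q.**

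- *Postoperative images.* Appendix B schedules 2D and 3D photography at Screening and at 6 months. The only scheduled postoperative 3D images are therefore taken at the appointment where the Breast Q is repeated. Neither 4.5 nor Appendix B gives an order. Review of these images could precede the questionnaire only within that one visit.
- *The preoperative simulation.* It already exists at surgery. A second look could take place at any time between surgery and the patient's own questionnaire. The documents neither describe nor exclude this.

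**Step 4. What the arm difference would estimate.** Let *c* be the effect of 3D imaging in the consultation on the 6-month Breast Q, and *p* the additional effect of postoperative review on top of it. The control arm has neither.

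- Questionnaire first: review cannot affect the score, so the expected difference is *c*, the quantity in 2.1.
- Review first for all 3D-arm patients: the expected difference is *c* + *p*.

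Both are valid randomised contrasts, but they answer different questions. The documents give no value for *p*, not even its sign.

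**Step 5. Whether the planned analysis could separate *c* from *p*.** Protocol 7.4 compares arms with χ², t and Mann-Whitney tests and with regression models. The SAP adds t or Wilcoxon tests, GEE for breast-level data and correlations. In the randomised cohort both exposures would follow the same allocation, so these methods see only the sum. If only some 3D-arm patients had the review, it would vary within the arm without being randomised, and Appendix B has no row for recording it.

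**The case against.** The best defence is that the clause is loose wording. It appears once, under secondary endpoints, between sentences about imaging all patients to obtain mammometric data. Its apparent purpose is to separate image capture, common to both arms, from review, which belongs to the 3D arm. The same paragraph ends by defining the groups by the preoperative consultation, every other section agrees, and 4.4 says that participation does not alter postoperative management. The missing timeline in Appendix A might also settle the timing.

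Most of this stands. It is why the point claims no more than an unresolved inconsistency, and why deleting the clause is the first remedy offered. It does not remove the point. The clause is in the current text, staff could follow it as written, and 4.5 leaves the order within the 6-month visit open.

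A second objection is that the comparison stays valid, so only a label is at issue. The validity is conceded. The label is the study's conclusion, however, since 2.1 asks about the consultation.

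**Conclusion.** The point holds in a limited form. The current text permits, but does not require, an arm-specific exposure before the unblinded, self-reported primary outcome. If that happened, a difference could not be credited to 3D imaging in the consultation. If the questionnaire comes first, nothing changes. The conclusion assumes that patients are the ones reviewing, and that Appendix A does not already fix the order.

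Three stronger readings are not supported:

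- A reader might infer that the randomised comparison is invalid. It is not: the two packages are compared fairly whatever the order.
- A reader might take the ± 60 days in Appendix B as a long exposure window. That tolerance dates the 6-month visit and its questionnaire. No text dates the review, and review of the scheduled postoperative images could come first only within that visit.
- A reader might want a size for the bias or a loss of power. The documents give nothing from which to derive either, and the sample-size statement in 7.3 does not bear on the question.

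This is a cheap improvement, not a threat to the trial's validity.

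**What to change.** The sponsor should decide which of three cases applies and edit accordingly.

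1. **No arm-specific postoperative review is intended.** Strike the reference to the postoperative period from the 7.1 sentence. It then agrees with 1.0, 2.1, 4.2, 4.4 and Appendix B.
2. **Review is intended, but not as part of the tested intervention.** State in 4.5 and 7.1 that every randomised patient completes the 6-month Breast Q before any arm-specific review of postoperative 3D images or morphing software. The order rule should also cover a second look at the preoperative simulation after surgery. Image capture is common to both arms and is unaffected.
3. **Earlier review is intended as part of the intervention.** Add it to 4.2 and Appendix B, reconcile it with 4.4, and restate the objective and conclusion as the effect of preoperative plus postoperative 3D review.

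Case 1 costs one deletion. Case 2 costs a sentence in each of two sections, with no extra visits, patients or staff. Its downside is that 3D-arm patients may see their review later, usually within the same visit, but longer if an earlier contact had been planned. Case 3 changes no procedure the sponsor intends, but gives up a conclusion about the consultation alone.
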